### 5.3.2 NUMBER OF PARTICIPANTS

Participants will be recruited using site records, databases and advertising materials (eg. posters, email scripts) approved by the ethics review board. All initial individual-targeted recruitment activities, such as any direct mailing of recruitment scripts, will be conducted by practice staff that are not directly involved in conducting the research. This separation will reduce any undue influence of the optometrist-patient relationship. This process will also

eliminate opportunity for the investigator to access personal health information before any consent for disclosure is provided by the potential participant.

It is anticipated that up to 80 potential participants may attend a Screening visit and up to 60 participants may be randomized and dispensed with study products, with a target of 53 completing the study.

### 5.3.3 INCLUSION AND EXCLUSION CRITERIA

---

A person is eligible for inclusion in the study if he/she:

1. Is at least 42 years of age and has full legal capacity to volunteer;
2. Has read and signed an information consent letter;
3. Self reports having a full eye examination in the previous two years;
4. Anticipates being able to wear the study lenses for at least 8 hours a day, 5 days a week;
5. Is willing and able to follow instructions and maintain the appointment schedule;
6. Habitually wears multifocal soft contact lenses, for the past 3 months minimum;
7. Has refractive astigmatism no higher than -0.75DC;
8. Is presbyopic and requires a reading addition of at least +0.75D and no more than +2.50D;
9. Can be fit and achieve binocular distance vision of at least 20/30 Snellen (or +0.20 logMAR) which participants also deem to be 'acceptable', with the available study lens parameters (sphere +4 to -6; near addition or LOW, MEDIUM, HIGH).

A person will be excluded from the study if he/she:

1. Is participating in any concurrent clinical or research study;
2. Habitually wears one of the study contact lenses;
3. Has any known active\* ocular disease and/or infection that contraindicates contact lens wear;
4. Has a systemic condition that in the opinion of the investigator may affect a study outcome variable;
5. Is using any systemic or topical medications that in the opinion of the investigator may affect contact lens wear or a study outcome variable;
6. Has known sensitivity to the diagnostic sodium fluorescein used in the study;
7. Self-reports as pregnant, lactating or planning a pregnancy at the time of enrolment;
8. Has undergone refractive error surgery or intraocular surgery.

\* For the purposes of this study, active ocular disease is defined as infection or inflammation which requires therapeutic treatment. Mild (i.e. not considered clinically relevant) lid abnormalities (blepharitis, meibomian gland dysfunction, papillae), corneal and conjunctival staining and dry eye are not considered active ocular disease. Neovascularization and corneal scars are the result of previous hypoxia, infection or inflammation and are therefore not active.

Age  $\geq 42$  years is an inclusion criteria because presbyopia is unlikely in persons aged  $<42$  years and, if present, may not be due solely to presbyopic changes representative of the wider population.

Pregnant and lactating women are not being excluded from the study due to safety concerns but due to fluctuations in refractive error, accommodation and/ or visual acuity that occur secondary to systemic hormonal changes. It has further been shown that pregnancy could impact tear production, which could impact dry eye symptoms. Such fluctuations could affect data, thereby negatively affecting study data integrity.

#### 5.4 STUDY MATERIALS

Habitual lenses: The optimized prescription of the habitual lenses will be determined by the investigator and the clinical site will order a new lens supply to the participant (6-pack for frequent replacement MF lenses, 30-pack for daily disposable MF lenses. If the participant wears the same prescription in both eyes, only one box will be ordered). If applicable, the clinic site will also supply the participant with a new bottle of their habitual care regimen including a new lens case.

Lens A and Lens B: CooperVision will provide each site with a small trial kit of Lens A lenses. Sites will source their own trial kit of Lens B. The sites will use these trial kits to fit Lens B and Lens A lenses to determine the optimal lens power. Once the final lens has been determined, the site will order a pack of 30 lenses for each eye with each lens type. Lens B will be ordered through the site's normal commercial route. CORE will coordinate the Lens A lens orders for each participant upon receipt of the lens order form, which is part of the study visit pack. If the optimization visit determines a different prescription is needed, a new lens supply will be ordered as described previously.

Reimbursement to practice sites for study product expenses will be provided by CooperVision at the end of the study, after CORE has reconciled the invoices and the product accountability and dispensing logs.

CORE will provide all sites with the study paperwork. This will include participant informed consent letters and study data collection forms, product accountability logs and the participant dispensing logs. CORE will train site personnel to complete the forms correctly and provide continued support to answer queries on correct form completion.

The primary contact for study products at CORE is:

#### 5.4.1 LENSES

---

Lens A is cleared by the by the United States Food and Drug Administration (FDA) and is not yet commercially available in the U.S.

Lens B is cleared by the by the United States Food and Drug Administration (FDA) and is commercially available in the U.S.

The table below lists the contact lens details for Lens A and Lens B including the lens parameters available for this study.

Table 1: Lens characteristics & parameter to be used

Lens	Lens A	Lens B
Manufacturer	CooperVision	Alcon
Material	stenfilcon A	delefilcon A
FDA Class	Group 5	Group 5
Sphere power (D)	+4.00 to -6.00 (0.25 steps), -	+4.00 to -6.00 (0.25 steps)
ADD power (D)	High, Medium, Low	Hi , Med, Lo
Base curve (mm)	8.4	8.5
Diameter (mm)	14.2	14.1

#### 5.4.2 OTHER PRODUCTS

---

Sodium fluorescein will be used to assess corneal and conjunctival staining.

#### 5.4.3 REWETTING DROPS

---

Participants will not be encouraged to use rewetting drops; however, those who habitually used rewetting drops will be allowed to continue using their normal drops.

#### 5.4.4 DISPOSING OF STUDY PRODUCTS

---

At the end of the study, all sites will return all unused products to CORE, unless otherwise directed. Worn lenses will be disposed of by participants and at the sites according to local regulations.

#### 5.4.5 PRODUCT ACCOUNTABILITY

---

Accountability logs must be kept by each site to include the number of contact lenses received and returned to CORE (where relevant). All products dispensed to participants must be recorded in participant dispensing logs.

### 5.5 SCHEDULED AND UNSCHEDULED VISITS

This study has a minimum of 12 scheduled study visits, including the screening visit, though some visits may be scheduled concurrently on the same day. There is an option for repeated screening and lens fitting visits as needed.

A scheduled follow-up visit may only take place when the participant attends wearing the study lenses for at least two hours. If this is not the case and the participant is not experiencing any problems with the lenses, the appointment will be rescheduled, ideally within the visit window.

[figure not shown]
Visits that fall outside of the specified visit windows will be designated as protocol deviations and at the end of the study, the data collected during protocol deviations will be assessed for their suitability to be included in the analysis population.

Table 3 summarizes the scheduled study visits and study codes.

Table 2: Summary of visits

Visit code	Approximate Duration	Visits
0	2 hr	Screening & Optimize habitual lens type & Fitting of study lenses
0/R1, 0/R2	As needed	Repeat Visit 0 if needed
Phase 1		
1-2	0.5 hr	Dispense optimized habitual lenses (Phase 1, 0-10 days after Visit 0)
1-3	0.5 hr	2-week follow-up habitual lenses (Phase 1, 14-16 days after 1-2)
Phase 2		
2-0	0.5 hr	Dispense Pair #1 (Phase 2, same day as 1-3)
2-1	0.5 hr	Optimize Pair #1 (Phase 2, 3-7 days after 2-0)
2-2	0.5 hr	Dispense (optimized) Pair #1
2-3	0.5 hr	2 week follow-up Pair #1 (Phase 2, 14-16 days after 2-2)
Phase 3		
3-0	0.5 hr	Dispense Pair #2 (Phase 3, same day as 2-3)
3-1	0.5 hr	Optimize Pair #2 (Phase 3, 3-7 days after 3-0)
3-2	0.5 hr	Dispense (optimized) Pair #2
3-3	0.5 hr	2 week follow-up Pair #2 (Phase 3, 14-16 days after 3-2)
EXIT	0.25 hr	Exit VA, exit forms & remuneration

Pair #1 and #2 will be either Lens A or B, as determined by the randomization table.

\*Visits could be subsequent on same day if CL power is unchanged

Participants will complete subjective ratings 'at-home' on day [REDACTED] 13 during each of the three 2-week lens wear periods (phases); anticipated to take a total of 20 minutes per phase. These ratings will be provided to the participants on visits 1-2, 2-2, and 3-2 respectively and will be returned and reviewed at visits 1-3, 2-3 and 3-3 respectively.

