#### 5.5.7 VISIT 2-2 DISPENSE (OPTIMIZED) PAIR #1

---

This visit may be conducted immediately following Visit 2-1 (if no prescription change is needed) or can be scheduled after Visit 2-1.

Participant to attend this visit wearing spectacles.

Procedures as follows:

1. Confirm participant's health and medications are unchanged.
2. [REDACTED]  
[REDACTED]  
b. [REDACTED]  
[REDACTED]  
[REDACTED]  
[REDACTED]  
[REDACTED]  
[REDACTED]  
[REDACTED]
3. [REDACTED]  
[REDACTED]  
[REDACTED]
4. After lenses have settled for at least 10 minutes continue with assessments
5. [REDACTED]  
[REDACTED]
8. [REDACTED]

9. [REDACTED]

10. Provide and explain to participant the subjective at-home rating forms to be completed on Day [REDACTED] 13 (Note: Day 1 is the day after the dispensing visit). Fill in the days and dates on these forms. Explain the ratings will include:

a. [REDACTED]

b. [REDACTED]

c. Ease of lens handling for insertion onto eyes (0 – 10 integer scale);

[REDACTED]

[REDACTED]

[REDACTED]

[REDACTED]

[REDACTED]

[REDACTED]

k. Ease of lens handling for removal from eyes (0 – 10 integer scale);

[REDACTED]

m. [REDACTED]

n. Report of any unusual symptoms or problems with lenses.

11. The participant will receive a 2-week lens supply and will be instructed to wear the lenses for at least 8 hours a day, 5 days a week.

12. The participant will be scheduled to return for Visit 2-3.

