#### 5.5.8 VISIT 2-3, 2-WEEK FOLLOW-UP PAIR #1

Participants will be asked to insert study lenses at least 2 hours prior to the visit.

This visit will occur 14-16 days (inclusive) after visit 2-2.

Assessments of lens Pair #1 will be conducted as described for habitual lenses at visit (Visit 1-3).

[REDACTED]

[REDACTED]

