## 6 MONITORING PROTOCOL ADHERENCE

Adherence to study visit windows, lens wearing schedule, and time windows around other data collection points (i.e. subjective ratings) will be monitored by CORE. Deviations from the study plan as described in the protocol will be reported in the study report. As described in Section 13.4, major protocol deviations will be reported to the Sponsor and Sterling Institutional Review Board within 7 days of becoming aware of them (as per Sterling Institutional Review Board guidelines).

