## 12 STATISTICAL ANALYSIS AND DATA MANAGEMENT

### 12.1 STATISTICAL ANALYSIS

All data will be analyzed by CORE at the University of Waterloo. Unmasked data analysis will be conducted using Statistica 10, Statsoft or other suitable software. Descriptive statistics will be provided on demographic data (age, gender, refractive error distribution, etc.). Table 7 lists the primary and other outcome variables and anticipated statistical procedures.

Comparisons will be made between the study lenses for the variables measured at the 2-week visits. Additionally the subjective ratings completed on day [REDACTED] 13 of each phase will be compared. A binomial test will be used to analyze the results for the count data [REDACTED]  
[REDACTED] Where relevant, the number of “neither agree or disagree” responses will be evenly distributed to the two options on the basis they would be equally likely to choose either.

Where appropriate, data may be presented as both mean and as counts by ‘bucket’ groups.

Table 6: Statistical procedures

Variable	Analysis	Statistical test
Ratings: Likert & Preference	Comparison between study days and/or between contact lenses per time point.	Freidman ANOVA Wilcoxon matched pairs test
Ratings: numerical ratings Biomicroscopy	Comparison between study days and/or between contact lenses per time point.	Freidman ANOVA Wilcoxon matched pairs test RMANOVA
Demographics Lens fit variables	Descriptive stats	One or more: mean, median*, mode, standard deviation, minimum, maximum, frequency count

\* For non-parametric data only

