## 12.2 DATA MANAGEMENT

Data will be collected and written on paper forms which will be provided to each site by CORE. Each site will email scanned forms to a designated person at CORE who will pass these scans to the data entry team. The site will endeavour to send the scanned forms to CORE on the same day as the study visit and at a maximum, two days after the study visit.

Data will be entered into a REDCap database developed and tested specifically for this study and accessible only to trained, authorised users. A data management plan will be developed to describe the data handling in more detail, including the personnel involved.

Data from this study will be retained by CORE for a minimum of 25 years on a password-protected server. After 25 years, data will be disposed of in accordance with the guidelines laid out by the University of Waterloo. More details regarding storage procedures are provided in section 15.7 and also in CORE SOP014\_v01\_Clinical data management.

At the completion of the study CORE will provide a copy of the study database in Excel format to the sponsor when requested. Data will typically be sent using a secure file share system operated by the University of Waterloo called Sendit which uses 128bit (or 256bit) SSL encryption. This system provides a secure way to transfer files when email is not appropriate, whether because of file size, file type or concerns over security. Sendit includes features such as password protection, a restricted time period for download, IP logging and email notification of download. Files may be encrypted prior to transmission at the request of the sponsor. Using this method means that data files are only stored on University of Waterloo servers during the transfer.

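### Does leaving out-of-window data to an end-of-study suitability review put the Lens A versus Lens B primary comparison at risk?

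*Combined protocol and SAP*

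**What the plan says.** Section 5.5 makes any visit outside its window a protocol deviation and adds that "at the end of the study, the data collected during protocol deviations will be assessed for their suitability to be included" in the analysis population. It gives no criteria, and Section 12.1 does not define that population. Section 12.1 also says "Unmasked data analysis will be conducted using Statistica 10, Statsoft or other suitable software".

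The primary outcome (Sections 3 and 4) is the at-home 0-10 rating of insertion handling on Day 13, compared between Lens A and Lens B. The forms are handed out at the dispensing visit, where staff are told: "Note: Day 1 is the day after the dispensing visit). Fill in the days and dates on these forms". The completed forms "will be returned and reviewed at visits 1-3, 2-3 and 3-3 respectively". For Pair #1 the follow-up timing is "This visit will occur 14-16 days (inclusive) after visit 2-2"; Section 5.5.12 sets the same interval for Pair #2.

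Section 6 says that visit windows, wearing schedule and "time windows around other data collection points (i.e. subjective ratings) will be monitored by CORE", and that deviations will be reported. Section 12.2 adds: "A data management plan will be developed to describe the data handling in more detail, including the personnel involved".

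**The concern.** The primary comparison is within participant, so excluding one person removes one A-minus-B difference. If nobody has said which off-schedule participants count, and the people deciding can see lens and rating, the analysis set could be shaped by the result. The nominal 5% error rate would then no longer hold exactly. In a comparison of the sponsor's lens with a competitor's, that would invite challenge.

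Two features make the worry plausible for the primary outcome. The rating form comes back at the windowed visit, so a visit deviation and a rating travel together. Section 6 also implies that ratings have time windows, yet no readable text gives a width for Day 13 or says what follows for the analysis if a rating is made on another day. Reporting deviations makes exclusions traceable but does not fix the set in advance.

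**Working it through.** **1. Does the rule reach the primary rating?**

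- Day 1 is the day after dispensing, so Day 13 falls 13 days after dispensing. The follow-up window is days 14 to 16. The gap is 14 − 13 = 1 day.
- Late visit (day 17 or later): the rating was due at least 17 − 13 = 4 days earlier, on a date already written on the form. The visit is mistimed; the rating is not.
- Early visit: on day 13 the visit coincides with the rating day. Before day 13 the rating is not yet due. Table 2 puts dispensing of Pair #2 on the same day as Visit 2-3, so a Visit 2-3 held before day 13 ends wear of Pair #1 before its rating is due. That is a missing value, not a value whose suitability someone can weigh.
- Section 12.1 compares the 2-week visit variables and then, as an additional item, the at-home ratings. Section 6 likewise lists visit windows apart from rating windows. The Section 5.5 sentence is about visits.

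So the literal reach is to the variables measured at the 2-week visits, not to the primary outcome.

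**2. The plan's own figure.** Inputs from Section 5.3.1: difference 5, SD 12.7 (0-100 scale), two-sided alpha 0.05, power 80%.

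- Normal approximation for paired data: n = [12.7 × (1.960 + 0.842) / 5]² = 50.6, so 51.
- Paired t-test (noncentral t, noncentrality 5/12.7 × √n): power is 79.5% at n = 52 and 80.3% at n = 53.

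The stated 53 is reproduced, with 12.7 acting as the SD of paired differences. On the 0-10 scale this is a difference of 0.5 with SD 1.27.

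**3. Size if the rule did reach the rating.** The documents give no rate of off-schedule participants. Assumption: k = 3 to 11 of 53 pairs (6% to 21%) are open to exclusion, independently of outcome, with no true difference. Simulation used normal paired differences and a t-test at two-sided 0.05. The second column counts a trial as positive if it is significant with all k in or with all k out. The last column gives power at the 0.5-unit target if all k are dropped from exactly 53.

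| k | Two-sided type I error, better of the two | Power with 53 − k pairs |
|---|---|---|
| 0 | 5.0% | 80.3% |
| 3 | 6.1% | 77.9% (50) |
| 5 | 6.5% | not tabulated |
| 8 | 6.8% | 73.3% (45) |
| 11 | 7.2% | 70.2% (42) |

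- False positives favouring Lens A alone are about half the second column: roughly 3.1% at k = 3 to 3.5% at k = 11, against 2.5%.
- Extreme bound, dropping only the flagged pairs unfavourable to Lens A: one-sided 3.6%, 4.6%, 6.4% and 9.0% for k = 3, 5, 8 and 11, against 2.5%.
- The power column assumes exactly 53 completers. Section 5.3.1 allows up to 60 to be randomised. If all 60 completed, power would be 85.1%; it would be 83.2% with 60 − 3 = 57 and 81.8% with 60 − 5 = 55. That margin is meant for dropout and may not be available.
- A rule chosen without sight of the results, and unrelated to outcome, leaves the error at 5%.

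**The case for a change.** The strongest case for a change is that the documents do not close the question. Section 6 expects some ratings to be off time, no readable text says how those are analysed, and the form is handed in at the windowed visit. The data management plan is described as covering data handling, not analysis populations. Section 14 names who reviews deviations, and Section 15.4 sorts them into major and minor, but for reporting rather than for inclusion. Masking the decision would not be simple either: site investigators know the lens, and "CORE will coordinate the Lens A lens orders for each participant upon receipt of the lens order form". A few sentences fixed in advance would cost little.

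Most of this stands as description: the detail is not in the readable text. It does not stand as a defect in the primary analysis.

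- Nothing says the suitability review uses lens codes or follows the comparison by lens. A review at the end of the study fits ordinary data cleaning before analysis, and the word unmasked is attached to the statistical analysis.
- Section 14 has deviations reviewed by the site Principal Investigator and CORE's Lead Co-ordinator, with data queries raised within 5 working days of receipt. Problems would therefore normally surface while the study runs.
- Whether the form records the date of completion cannot be tested. The forms are not among the documents, and several rating items in Sections 5.5.3 and 5.5.7 are redacted.
- The data measured at the 2-week visits are exposed to the rule, but the primary hypothesis does not rest on them, and Section 15.4.3 requires every deviation to appear in the final report.

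**Conclusion.** The gap is real but is one of missing detail, and no change to the plan is needed. On the literal wording, the effect on the primary test is nil. The increase to 6.1%-7.2% needs three things together: the visit rule being stretched to cover an at-home rating, 3 to 11 pairs being affected, and someone choosing the analysis set after seeing both results. The documents establish none of these.

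The sensible default follows from the plan as written: keep every participant with Day 13 ratings for both lenses in the primary comparison whatever the visit date, settle the handling of mistimed visit data before lenses are compared, and list the deviations as Sections 6 and 15.4.3 already require. This conclusion assumes an ordinary deviation review of that kind. It would change if the review were shown to follow the comparison by lens and to remove Day 13 ratings.

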### 5.5.1 VISIT 0, SCREENING & FITTING VISIT

Informed consent shall be obtained in writing from the participant and the process shall be documented before any procedure specific to the clinical investigation is carried out.

Participants will be assigned a unique alpha-numeric study ID after they sign the consent documentation i.e. before their eligibility for the study has been confirmed. Each site will use a different letter preceding the participant ID number. For example, participant 01 at site W will be W-01, and participant 01 at site Z will be Z-01. Ineligible participants will be discontinued from the study.

The investigator will determine participant eligibility using the inclusion and exclusion criteria. The study procedures are outlined below:

1. The participant is expected to insert their habitual multifocal contact lenses at least 2 hours before attending the visit and if available bring an additional (new) pair of lenses. (If participant habitually wears daily disposable MF lenses, ask if a 2-week supply is available. All habitual lenses used during the study will be replaced at no charge to the participant.)
2. The participant will be required to read and sign an Informed Consent Form prior to enrollment. When the participant has signed the consent form, the participant will be considered enrolled in the study and will be assigned a study ID.
3. Participant demographics and medical history (age, sex, race, ethnicity, medical conditions, medications, allergies).
4. Contact lens history (habitual lens information and wearing habits).
5. [REDACTED]
6. [REDACTED]
7. The participant removes their habitual contact lenses.
8. [REDACTED]
9. [REDACTED]
10. [REDACTED]

11.

13. The investigator will fit both study lenses (Lens A and Lens B) using fitting sets following to the manufacturers fitting guidelines.

